Aim 2. To compare the effect of PGx testing offered as a stand-alone or as part of medication therapy management (MTM) with respect to patient, pharmacist, pharmacy setting variables. Using a cluster randomized study design, pharmacies will be randomized to provide PGx testing only or PGx testing with MTM. Study outcomes will be gathered through pharmacist and patient surveys and follow-up interviews with pharmacists. The primary goal of the clinical trial is to study the difference between the effects of these two services on patient acceptance, comprehension, satisfaction, and medication adherence; secondary outcomes include acceptance of recommendations for drug/dosing changes (AIM 2a). The second part of this aim will evaluate pharmacist and pharmacy variables relevant to the sustainability of these delivery models (AIM 2b).

[figure not shown]
- 2a) Patient perceptions are increasingly used to assess quality of care. We will compare and assess patients’ 1) satisfaction with testing experience in a pharmacy setting and perceived value of testing; 2) comprehension of test result; and 3) medication changes and adherence. We will collect demographic information that may be associated with patients’ satisfaction, comprehension and perceived value of PGx testing, such as age and education status as well as information about past experiences with prescribed medications. Data will be collected through a baseline and one follow-up survey. We hypothesize that patients overall will be satisfied with PGx testing provided through the community pharmacy, particularly those who have experienced adverse responses or a poor outcomes, are taking multiple medications, and are older. Furthermore, we hypothesize that patients’ increased awareness about their genetic risk to adverse responses will result in improved medication adherence and sharing of results with other providers. Patients with lower education status, chronic illnesses, and who are older may report greater benefit from PGx testing delivered as part of an MTM, with respect to comprehension and overall satisfaction. We will also assess whether patients’ perceived value or satisfaction was influenced by the presence/absence of PGx variants.

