- In-person MTM (required only of pharmacists randomized to MTM + PGx testing arm): The purpose of this CE is to review elements of MTM, development of medication action plans, and incorporation of PGx testing into an MTM session. The development of this module was adapted from the MTM module offered by the American Pharmacists' Association (APhA). Attendance may be waived if the pharmacist provides proof of completion of the APhA MTM CE program.

PART II. PHARMACOGENETIC TESTING IN COMMUNITY PHARMACY TRIAL

Part II of the study will involve the cluster randomized trial to compare the effect of PGx testing as a stand-alone service to PGx testing with MTM (Figure 1/Aim 2)). We aim to enroll 20 pharmacist (in 20 separate pharmacies) and 360 patients in the study (~18 per pharmacy).

PGx Testing. Testing will be available for patients with active prescriptions for the drugs listed in Table 1. The drugs were selected based on CPIC guidelines and/or drug labels with PGx information that are likely to be filled at community pharmacies. If new CPIC guidelines are developed by the start of the study, we will update the list accordingly. Testing for each of the genes listed in the table will be provided by the CLIA-certified laboratory Pathway Genomics (CLIA # 05D1092505; San Diego, CA). The test for this study is a customized panel test that includes CYP2D6, CYP2C19, CYP2C9, SLC01B1 and VKORC1/CYP2C9. Currently, turnaround time for testing is 7-10 days. Given the varying coverage policies for PGx testing, all test fees will be supported by the study.

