Survey Data Analysis. Analysis of data collected from surveys will be conducted using a software package such as STATA. We will calculate frequency data and statistical associations for the respondent characteristics. Both univariate and multivariate analyses will be conducted for hypotheses (see below). Because the trial uses a cluster design, the analysis will use logistic mixed effects regressions by including treatments as the fixed effect of interest and clusters as random effect. We will first test if the random effect is significant or not. If not, then we will use regular logistic regression to perform the analysis; if significant, we will continue using mixed effect logistic model. In either case, odds ratios and 95% confidence intervals will be generated to assess strength of associations between treatments and outcomes. A secondary analysis will be performed in which the comprehension outcome is not collapsed into “correctly identifying the presence of any variant versus no variants”, but will include correctly indicating the result for each gene (e.g., slow/fast metabolism vs. average). In this case, a logistic random effects model will also be applied with pharmacist and patient as random effects. If a sufficient number of patients are enrolled per drug, a stratified data analysis by drug will be performed to detect any differences regarding comprehension, adherence, or satisfaction. In addition, the impact of time to treatment will be assessed on patient satisfaction and adherence.

- We hypothesize that patients will have a higher level of comprehension of test results from the MTM plus PGx testing than those receiving testing offered as a stand-alone service.
- We hypothesize that patients overall will be satisfied with PGx testing provided through the community pharmacy and likely to have testing again in this setting
- We hypothesize that patients will find PGx testing beneficial, particularly those who have experienced adverse responses or a poor drug outcome in the past, are taking multiple medications, and are older.
- We hypothesize that patients' increased awareness about their genetic risk to adverse responses will result in improved adherence through assurance about the effectiveness and/or safety of their medications.
- We hypothesize that the additional time required to deliver PGx testing as part of an MTM session may present a barrier to providing PGx testing through this approach.

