Sensitivity analyses will be performed to examine the impact of reported changes in comprehension, as individuals who drop out could potentially be less likely to change behaviors. The results of complete case and imputed analyses will be reported. The type of missing data will be examined to understand whether they are missing at random (MAR) or not. If they are, then the assumption will be that the imputed analyses provide the better estimate of the treatment differences. If the decision is that one cannot say that the data were MAR, then both results will be presented with accompanying text describing the potential biases in both sets of results, the level and type of missingness seen, as well as the limitations of interpretations if a significant number of observations were missing.

STUDY SAFETY MEASURES

Safety Measures

This study does not contain any safety endpoint measures.

Pregnancy Guidelines

Pregnant females are eligible to participate in this study if they meet the inclusion criteria. There is no known risk to the mother or unborn child as a result of this study.

Safety Monitoring

Federal regulations require prompt reporting to the IRB, appropriate institutional officials, sponsor, coordinating center and the appropriate regulatory agency head of unanticipated problems involving risks to subjects or others that occur in the course of a subject's participation in a research study at DUHS. (45 CFR 46.103(b)(5)(i) and 21 CFR 56.108(b)(1)).

Investigators are responsible for monitoring the safety of patients who have entered this study and for alerting the study team to any event that seems unusual, even if this event may be considered an unanticipated benefit to the patient.

The Principal Investigator will continuously monitor and tabulate adverse events. Appropriate reporting to the Duke University Medical Center IRB will be made. The Principal Investigator or designee will also continuously monitor the conduct, data, and safety of this study to ensure that:

- Interim analyses occur as scheduled;
- Risk/benefit ratio is not altered to the detriment of the subjects;
- Appropriate internal monitoring of adverse events and outcomes is done;
- Over-accrual does not occur;
- Under-accrual is addressed with appropriate amendments or actions;
- Data are being appropriately collected in a reasonably timely manner.

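### The primary comprehension analysis drops the pharmacy random effect after a non-significant pre-test, so its nominal 95% interval under-covers if there is modest clustering

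*Combined protocol and SAP*

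**What the plan says.** Aim 2 sets the unit of randomization: "pharmacies will be randomized to provide PGx testing only or PGx testing with MTM". Part II plans 20 pharmacies with about 18 patients each, 360 in all. Part III (Comprehension of Results) makes comprehension the primary outcome and scores it correct or incorrect.

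Under Data Analysis, Survey Data Analysis, the model is first chosen on the right ground: "Because the trial uses a cluster design, the analysis will use logistic mixed effects regressions", with treatment as fixed effect and cluster as random effect. The next step makes that choice conditional: "We will first test if the random effect is significant or not. If not, then we will use regular logistic regression to perform the analysis". The mixed model is kept only if the test is significant. The result is reported the same way on both branches: "In either case, odds ratios and 95% confidence intervals will be generated to assess strength of associations between treatments and outcomes". The directional hypothesis served by this analysis is stated in the same section: "We hypothesize that patients will have a higher level of comprehension of test results from the MTM plus PGx testing".

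The plan does not state the type or level of the pre-test, the reference distribution for the interval, or an ICC.

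**The concern.** Regular logistic regression treats the patients as independent. Whether they are follows from how the trial was randomized and delivered, and a p-value from 20 clusters is weak evidence on the matter. The protocol also gives reason to expect some clustering. It asks for one pharmacist per pharmacy, leaves the communication of results to that pharmacist's discretion, and lets toolkit use follow the pharmacist's preference. The primary outcome is whether the patient understood what that pharmacist communicated.

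If modest clustering goes undetected, the standard error of the treatment log odds ratio is too small, and the reported interval covers less than the promised 95%. Nothing else in the plan repairs the main interval. The passage beginning "Sensitivity analyses will be performed to examine the impact of reported changes in comprehension" deals with missing data. The per-gene secondary analysis keeps pharmacist and patient random effects with no pre-test, but it addresses a different outcome.

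**Working it through.** **Inputs from the documents.** 20 pharmacies, about 18 patients each (20 × 18 = 360, which agrees with the stated total), a binary primary outcome, 95% intervals. A 10 v 10 split is implied by the Pharmacist Study Population and interview sections. The power calculation behind 18 per cluster cannot be reproduced, because no ICC, effect size, base rate, alpha or power is given.

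**Assumptions.** ICC from 0 to 0.20 on the proportion scale; 70% correct; 18 analysed per pharmacy; likelihood-ratio pre-test at 5% against a 50:50 chi-square mixture; Wald z intervals on both branches.

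**Step 1, hand check of the dropped branch.** Design effect = 1 + (18 − 1) × ICC. At ICC 0.01 / 0.02 / 0.05 this is 1.17 / 1.34 / 1.85. The regular-logistic standard error is too small by the square root: 1.08 / 1.16 / 1.36. The error of a nominal 5% test is then P(|Z| > 1.96 ÷ that factor), about 7.0 / 9.0 / 15.0%.

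**Step 2, simulation of the whole rule with no true difference.** Logistic-normal data with between-pharmacy variance ICC × p(1 − p); random-intercept model fitted by maximum likelihood; 40,000 runs per setting (simulation SE 0.11 to 0.15 points). Error means that the nominal 95% interval excludes an odds ratio of 1. Entries are percentages, except the pre-test row, which is in percentage points and comes from unrounded rates.

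| ICC | 0 | 0.005 | 0.01 | 0.02 | 0.05 | 0.10 | 0.20 |
|---|---|---|---|---|---|---|---|
| Random effect dropped | 97.9 | 95.8 | 92.9 | 83.9 | 47.5 | 11.7 | 0.6 |
| Error when dropped | 4.9 | 6.0 | 7.0 | 8.9 | 15.4 | 24.6 | 36* |
| Error when kept (z) | 0.7 | 1.3 | 1.9 | 2.3 | 4.1 | 6.2 | 7.8 |
| **Two-step rule, overall** | 4.8 | 5.8 | 6.6 | 7.8 | 9.5 | 8.4 | 8.0 |
| Always mixed, z | 4.4 | 4.9 | 5.6 | 6.2 | 7.4 | 7.6 | 7.9 |
| Added by the pre-test | 0.5 | 0.9 | 1.0 | 1.6 | 2.1 | 0.8 | 0.0 |
| Pre-test left in, t(18) in mixed branch | 4.8 | 5.8 | 6.6 | 7.7 | 8.8 | 6.9 | 6.1 |
| Always mixed, t(18) | 3.1 | 3.5 | 4.1 | 4.6 | 5.6 | 5.8 | 6.1 |

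*From 239 runs only. The two-sample t-test on pharmacy proportions gave 4.9 to 5.1% throughout.

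The overall rate is the weighted mean of the branches. At ICC 0.05: 0.475 × 15.4 + 0.525 × 4.1 = 9.5. At ICC 0.02: 0.839 × 8.9 + 0.161 × 2.3 = 7.8. Coverage of the reported interval is therefore 93.4 / 92.2 / 90.5 / 91.6 / 92.0% at ICC 0.01 / 0.02 / 0.05 / 0.10 / 0.20.

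**Step 3, a separately coded check.** Beta-binomial data at 70% correct (20,000 runs) gave 6.8 / 7.8 / 9.5 / 8.3 / 7.6% for the two-step rule at the same five ICCs, with the pre-test adding 0.0 to 2.1 points. At ICC 0 the rule was close to nominal.

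**Step 4, sensitivity of the two-step error at ICC 0.01 / 0.02 / 0.05 / 0.10 / 0.20 (%).**
- Plain 1-df chi-square pre-test: 6.8 / 8.2 / 10.3 / 8.9 / 8.0
- Pre-test at the 20% level: 6.0 / 6.8 / 7.8 / 7.7 / 7.9
- Unequal clusters (CV 0.5): 6.8 / 8.6 / 9.8 / 8.7 / 9.8
- 12 respondents per pharmacy (the follow-up survey is opt-in): 6.1 / 6.8 / 8.6 / 9.1 / 7.5
- 60% correct: 6.4 / 7.6 / 8.8 / 7.7 / 7.9
- 80% correct: 6.3 / 7.7 / 9.6 / 8.3 / 9.1

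With the ICC defined on the latent logistic scale instead, the range is 5.3 to 9.4%.

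**The case against.** The strongest reply is that most of the excess does not come from the pre-test. Always keeping the random effect with z already gives 5.6 to 7.9%, and at ICC 0.10 and above nearly all the excess comes from a z reference that the plan never names. The pre-test's own share also depends on its unstated level. At 20% it falls to 6.0 − 5.6 = 0.4, 6.8 − 6.2 = 0.6 and 7.8 − 7.4 = 0.4 points at ICC 0.01, 0.02 and 0.05. The documents supply no ICC, and at zero the rule is sound, so the remedy would only cost power there. The Purpose section describes an exploratory study, with no alpha or decision rule.

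Much of this stands as a limit on size. The pre-test's share is about 0 to 2 points (about 3 with a plain chi-square pre-test), and the harm is to the reported interval, with no stated decision rule at risk. The intervals are too narrow on average, not on every branch: when the effect is kept at low ICC they over-cover. None of this defends the rule. The plan promises a 95% interval on either branch, and the fallback discards the trial's randomization structure on evidence too weak to support doing so. Leaving the reference unnamed is a gap that the same edit should close.

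**Conclusion.** The concern holds and should be corrected before the outcome data are analysed, since a later change would look data-driven. For an ICC of about 0.01 to 0.20, the rule with Wald z gives a nominal 95% interval that misses a null effect in about 6.6 to 9.5% of trials, worst near 0.05. There is no excess at ICC 0 and little at 0.005 (5.8%).

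Only the 95% level, the 20 pharmacies and the roughly 18 enrolled in each come from the documents. The alternatives tried move the range to about 5.3 to 10.3% with equal clusters, and up to 10.8% with unequal clusters and the chi-square pre-test. The conclusion covers outcomes analysed by logistic regression, chiefly comprehension. It does not extend to the continuous satisfaction scales or the refill-based adherence ratios.

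**What to change.** Delete the pre-test and the switch to regular logistic regression. Suggested text:

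> The primary analysis is the mixed-effects logistic model. The pharmacy random intercept will be kept whatever its estimated variance or p-value. The 95% CI for the treatment odds ratio (and any p-value) will use a t reference with degrees of freedom equal to the number of pharmacies analysed minus 2 (18 for 20 pharmacies), less one for each pharmacy-level covariate. A two-sample t-test on the pharmacy proportions correct will be reported as a prespecified check.

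The covariate clause is needed because "Both univariate and multivariate analyses will be conducted for hypotheses". Both changes are needed. With the pre-test left in, t(18) alone still gives 6.6 / 7.7 / 8.8% at ICC 0.01 / 0.02 / 0.05. With z retained, deleting the pre-test alone leaves up to 7.9%. The mixed model stays primary, and governs, because it yields the odds ratio the plan promises. The check is worth having because t(18) ran at about 3 to 6% with equal clusters but reached 7.7% at ICC 0.20 with unequal ones, while the pharmacy-level test held about 5%.

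**Cost.** A few sentences and no new data. Compared with the two-step rule, log-odds intervals are on average 11 / 13 / 15 / 14 / 9 / 7% wider at ICC 0 / 0.01 / 0.02 / 0.05 / 0.10 / 0.20; 7% of that is the multiplier (2.10 ÷ 1.96 = 1.07). For an assumed 60% v 75% correct at ICC 0 / 0.02 / 0.05 / 0.10, power is 85 / 80 / 68 / 52% under the two-step rule, 80 / 72 / 60 / 46% with t(18), and 82 / 71 / 57 / 43% for the pharmacy-level test. Above ICC 0, part of that gap is power gained by exceeding 5% error. At ICC 0 the loss is real.

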- **MTM Session #2:** The follow-up MTM session will be conducted either in-person or by phone as deemed appropriate by the pharmacist and feasible for the patient to return to the pharmacy. Our experience with pharmacist reporting of PGx test results indicates that results can be discussed in an average of 15 minutes (see section C.2.a). Telephonic MTM has been found to be as effective as in-person MTM with respect to outcomes and patient satisfaction.⁷⁸⁻⁸¹ Prior

to MTM#2, the pharmacist will review the PGx results and the patient's medication history to determine if drug or dosage adjustments are indicated based on the results. If the patient is taking another medication impacted by one of the PGx genes tested and there is strong evidence regarding dose adjustment/drug selection based on genotype, recommendations for additional drug changes/dose adjustments will also be communicated to the patient and ordering provider. The patient and pharmacist will review the information provided in the previous session, possible medication changes, PGx test results and its significance to current treatments, and strategies to improve adherence. The pharmacist will also discuss how the results may be important for future medications. Patients will be provided a copy of the MAP and a summary card of their PGx results will be filled out for the patient to retain. The pharmacist will also contact the prescribing physician with recommendations based on the results and a copy of the MAP. All final treatment decisions will be made by the physician.

Table 1. Drugs eligible for trial

Drug	Gene	CPIC	FDA Label	Test Interpretation/Utility
Aripiprazole	CYP2D6	No	Yes	The drug's half-life approximately doubles in poor metabolizers compared to extensive; the dose for poor metabolizers should be decreased to minimize side effects. ^{82,83}
Carisoprodol	CYP2C19	No	Yes	Patients with reduced metabolism should use caution while on carisoprodol. Poor metabolizers of CYP2C19 have a 4-fold increase in exposure to carisoprodol and a 50% decreased exposure to meprobamate (a metabolite of carisoprodol) compared to normal CYP2C19 metabolizers ⁸⁴
Celecoxib	CYP2C9	No	Yes	Half-life was 2.7-fold higher in subjects with CYP2C9 *3/*3 (Poor Metabolizer) than in extensive metabolizers. Patients who are poor CYP2C9 metabolizers should be administered celecoxib with caution and a dose reduction of 50% should be considered. ⁸⁵

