and can read and write in English, and have a new or existing prescription (<1 year active) for a drug listed in Table 1 to be eligible to participate. Each pharmacy will identify existing patients eligible for testing through a query of their database for active prescriptions for the selected drugs. If more than 30 patients in a pharmacy are identified by the database search, we will ask pharmacists to contact patients with the newest prescriptions. Patients will be contacted by phone or in-person by the pharmacist to introduce the study. Interested patients will be asked to visit the pharmacy to learn more about testing, sign the consent form requested by the testing laboratory, and provide a DNA sample (buccal swab). Patients who have had PGx testing for one of the genes in Table 1 or had an MTM within the past 12 months will be ineligible. All women and minorities who meet the study inclusion criteria will be eligible to participate in the study. Based on our power calculations, we estimate that we would need to enroll 18 patients per cluster (360 total).

Patients who consent to testing based on their pharmacist's recommendation will be asked to provide a buccal swab for DNA extraction. Patient samples will be sent for testing to Pathway Genomics laboratory. Testing will be provided at no cost for participants. As the Pathway Genomics' clinical tests are currently available to any clinician, only the consent required by the testing lab will be required of the patient.

Patients in the control arms will be identified by each participating pharmacy; two controls will be identified per each participant in the PGx arms (2:1) and matched on drug, age and gender. Time on treatment, medication changes (dose/drug selection), and refill history (adherence) data will be collected along with demographic data and compared to patients in the PGx testing arms. Based on their pharmacy records, patients who have undergone MTM or PGx testing outside of the study will be excluded from the control arm.

Risk/Benefit Assessment. If patients decide to have pharmacogenetic testing, a buccal swab sample is required. There are no known risks to a buccal swab sample. The sample, or DNA extracted from the sample, will be sent to the laboratory and stored only for the time necessary laboratory regulations.

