The integration of PGx testing into the community pharmacy setting will be assessed primarily through surveys of patients and pharmacists. In addition, we will conduct semi-structured interviews with a subset of pharmacists to gather more in-depth understanding of their experiences, perceived barriers, and likelihood to continue to offer PGx testing. The measures to be assessed are described below; clinical outcome measures will be collected about the medications impacted by PGx only.

Patient Surveys (Aim 2b) The baseline survey will collect demographic data, prior knowledge about PGx, self-reported co-medications, time on treatment for PGx-related drug(s), and medication adherence (see Table 2; Appendix 5). The follow-up survey will gather data on 1) satisfaction with the testing experience in a pharmacy setting, including use/provision of patient materials from Aim 1; 2) perceived value of testing; and 3) comprehension of test result. Additional measures include medication-taking behaviors and information-sharing. The follow-up survey will be administered approximately one month after the PGx results are communicated since many of the medications are prescribed in 90-day allotments. Key survey questions are further described below; data on age, gender, co-medications, and time on treatment for PGx-related drug(s) will also be collected for controls.

- [Baseline] Literacy. We will screen for health literacy using the validated single question: “How confident are you filling out forms by yourself?” Compared to the gold standard literacy tools REALM or S-TOFHLA, this single question accurately predicts inadequate health literacy⁹⁹ and is more feasible to administer.
- [Follow-up] Comprehension of Results. Our primary outcome will be comprehension of test results based on gist recall of the phenotype.¹⁰⁰ Specifically, the outcome of interest is the patient’s recognition of the presence or absence of a variant gene. Due to the complexity of genotypes and presumed patient unfamiliarity with gene nomenclature, we do not believe it reasonable to expect patients to recall their genotype. Therefore, we will instead ask patients to circle their specific metabolizer status (e.g., rapid, extensive, intermediate, poor, or inconclusive). For the genes *SLCO1B1* and *VKORC1*, we will ask patients to indicate their test

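### By-drug differences and the stated effect-modification hypothesis have no named interaction test; separate per-drug strata of undefined minimum size are likely to mislead

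*Combined protocol and SAP*

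**What the plan says.** The by-drug analysis appears in DATA ANALYSIS, Survey Data Analysis. It is conditional: "If a sufficient number of patients are enrolled per drug", then "a stratified data analysis by drug will be performed to detect any differences regarding comprehension, adherence, or satisfaction". No number defines sufficiency. The main model described there is a mixed logistic regression with treatment as the fixed effect of interest and cluster as random effect. No treatment-by-drug term and no multiplicity control are named.

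STUDY OBJECTIVES, Aim 2a, adds a hypothesis about who gains most: "Patients with lower education status, chronic illnesses, and who are older may report greater benefit from PGx testing delivered as part of an MTM". The list of hypotheses in Survey Data Analysis does not carry this one over.

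On data, PART III, Patient Surveys, states: "The baseline survey will collect demographic data, prior knowledge about PGx, self-reported co-medications, time on treatment for PGx-related drug(s), and medication adherence". Table 2 outlines the survey content. Neither lists chronic illness by name. The instrument itself is Appendix 5, which is not in the text supplied.

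**The concern.** Whether an effect differs between drugs is a question about a contrast between strata. A significant result for one drug and a non-significant one for another does not answer it, because that pattern arises readily when the true effect is the same in both. An arm-by-drug interaction addresses the question directly.

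The Aim 2a hypothesis has the same structure: MTM is expected to help some patients more than others. A treatment term, even adjusted for age and education, does not test it.

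At stake are two secondary conclusions. The trial could report that pharmacist-delivered testing with MTM works for some drugs and not others when nothing of the kind is true, and its own effect-modification hypothesis could be settled by whichever analysis is chosen after the data are seen. The primary arm comparison is not affected.

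**Working it through.** **Inputs from the documents**
- Size (PART II, opening): "We aim to enroll 20 pharmacist (in 20 separate pharmacies) and 360 patients in the study (~18 per pharmacy".
- Basis (PART II, Patient Study Population): "Based on our power calculations, we estimate that we would need to enroll 18 patients per cluster (360 total".
- Arms (Aim 2): "pharmacies will be randomized to provide PGx testing only or PGx testing with MTM", hence two tested arms. Ten pharmacies per arm is inferred from the recruitment and interview sections.
- Drugs: ten rows under "Table 1. Drugs eligible for trial".
- Outcomes in the by-drug analysis: three.

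**Assumed, not in the documents:** comprehension of 60% v 75% (alternative 60% v 80%), the same for every drug; two-sided 5% tests; clustering ignored unless stated; no dropout; each patient in one drug stratum.

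**1. The plan's own figure.** 20 × 18 = 360, which agrees. The power calculation behind 18 per cluster cannot be rerun, because the text gives no effect size, rates, intracluster correlation (ICC), alpha or power.

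**2. Stratum size if drugs are evenly spread.** 360 / 10 = 36 per drug; 36 / 2 = 18 per arm per drug. The documents' own 18 is patients per pharmacy, a different quantity.

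**3. Chance of a mixed pattern under a uniform effect.** With K drugs and per-drug power q, the chance that some but not all are significant is 1 − q^K − (1 − q)^K. Here q is the exact binomial power of the pooled two-proportion test at 60% v 75%.

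| Drugs (K) | Per arm per drug | q | Chance of a mix |
|---|---|---|---|
| 10 | 18 | 0.164 | 1 − 0.164^10 − 0.836^10 = 83% |
| 4 | 30 | 0.230 | 1 − 0.230^4 − 0.770^4 = 65% |
| 3 | 60 (all 360 patients) | 0.425 | 1 − 0.425^3 − 0.575^3 = 73% |

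Simulation of the ten-drug case with an assumed ICC of 0.05 gave about 81%, so clustering does not change the picture.

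**4. Chance of a false positive with no effect.** Ten independent tests (one outcome): 1 − 0.95^10 = 40%. Simulated values for ten drugs at 18 per arm were 40–47% without clustering and 46–52% at ICC 0.05 with unadjusted tests.

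**5. What could count as sufficient.** For 80% power within one drug (normal approximation, pooled variance), 60% v 75% needs 152 per arm, or 304 of the 360 patients: at most one drug. For 60% v 80% it needs 82 per arm, or 164 per drug; 360 / 164 = 2.2, so at most two drugs.

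**6. One joint test instead.** In the same simulations (ten drugs, 18 per arm), a single heterogeneity test (Cochran Q on log odds ratios) rejected in 1–3% of runs when the effect was uniform. It is conservative and weak at this size. With five drugs at no effect and five at 60% v 80%, it rejected in about 31% of runs.

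**The case against.** The strongest reply is that the analysis is conditional, so sparse strata may never be analysed. This stands in part: 18 per arm per drug is an even-spread assumption, and no expected drug mix is given. A reader might infer that the plan commits to ten analyses at 18 per arm and will show false differences. The documents support neither. But the condition has no number, and the mixed pattern remains likely with three or four better-filled strata.

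The sentence is also ambiguous. It could mean arm differences within a drug, outcome differences between drugs, or differences in arm effect between drugs. Only the last requires an interaction test, and the criticism is confined to that reading.

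Small strata mainly cause low power; the number of tests drives the false-positive rate. Under a uniform effect, the significant drugs are true positives. The error lies in reading the contrast with the others as a difference. A reader might multiply ten drugs by three outcomes and quote 1 − 0.95^30 = 79%, but that needs independence, and the three outcomes come from the same patients.

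On Aim 2a, it would be too strong to say that effect modification can never be tested. Univariate and multivariate analyses are promised, and naming treatment as the effect of interest does not exclude other terms. What holds is that no interaction is specified. Likewise, a reader might infer from Table 2 that chronic illness is not recorded. An outline cannot show that while Appendix 5 is unseen.

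Finally, without shrinkage a joint model gives per-drug estimates nearly as noisy as the strata, and its interaction test is weak. That is correct, and it limits what the fix can deliver.

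**Conclusion.** The point holds in a limited form. If the by-drug analysis is meant to show whether the arm effect varies by drug, the planned strata do not test that, and the undefined sufficiency condition does not cure it. Under an assumed uniform 60% v 75% effect without clustering, a mix of significant and non-significant drugs has a probability of about 65–83% across the scenarios examined. With no effect, ten independent tests carry a 40% chance of at least one false positive. The rates and the spread over drugs are assumptions; the conclusion does not depend on 18 per arm.

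Separately, the Aim 2a effect-modification hypothesis has no specified test. Both gaps concern secondary analyses and are inexpensive to close.

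**What to change.** Replace the stratified analysis with one model per outcome (logistic for comprehension, linear for scale outcomes) containing arm, drug or gene group, arm × drug, and a pharmacy random effect. Report the joint interaction test first, then per-drug estimates with 95% confidence intervals, preferably shrunken by treating arm-by-drug as random. State in advance:
- which contrast the by-drug analysis addresses;
- the minimum number per drug, or the grouping by gene;
- how patients on more than one eligible drug are classified.

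Test the Aim 2a hypotheses as arm × education, arm × age and arm × chronic illness. Confirm that Appendix 5 records chronic illness, and add an item only if it does not.

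Label all of this exploratory, and state that a non-significant interaction does not show equal effects, because power is low.

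The cost is analysis wording and possibly one survey item. Enrolment, the interventions and the primary endpoint are unchanged. The downside is that per-drug claims become weaker.
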